Analysis: We will compare and contrast both network and nodal attributes based on sex and race/ethnicity. We will use a multivariable linear regression to test if gender and race can predict clustering coefficient while controlling for age, HD vintage and socioeconomic status. We will refine our network model by adding and removing links with each wave of the survey. For the nodal attributes that are continuous variables, standard tests of hypothesis such as t-test, ANOVA, and linear regression will be used. For categorical attributes, ANOVA density-models as well as logistic regression models will be used. For continuous variables, testing distances and similarities, Moran statistics will be calculated. Since the observations are not independent observations drawn at random from a large population, we will use a boot-strap approach for estimating the variation of estimates from a large number of random sub-samples of network members⁵⁰⁻⁵².

Limitations: Having patients self-report their own social links, while an established methodology, can still be subject to recall bias⁵¹. Thus, we will use observations of social interactions for verification using the aforementioned log. These observations will be used to weight the survey generated links.

Approach to AIM 2: Using network information from AIM 1, we will examine how structural differences in social networks affect knowledge, attitudes, and behaviors towards kidney transplantation. **H2:** Patients with dense HD social networks have similar attitudes (both positive and negative) about transplantation and completion of steps to kidney transplant as compared to patients diffuse networks.

Rationale: We have found the primary barrier to the transplant wait-list is the completion of the work-up^{1,4}. Previous research shows that patients in small dense networks share similar ideas⁴². This could either positively^{1,26} or negatively¹⁰ affect access and progress to kidney transplantation. We are using steps completed to measure progress to transplantation; a measure has been established for transplant disparity research to improve the granularity of the measurement and compare results across studies².

Step	Description
1	suitability for referral to transplant center
2	interest in transplantation
3	referral call to transplant center
4	first visit to transplant center
5	transplant center work-up
6	work-up complete
7	active on the list
8	successfully received a kidney transplant

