AIM3: Compare and contrast the diffusion of knowledge, attitudes, and behaviors regarding transplantation through HD social networks by targeting either the most central or the most clustered members of the network to disseminate a transplant education intervention. **H3:** Targeting patients with high clustering coefficients will be the most effective method for the spread of knowledge and favorable attitudes toward transplantation, and completing steps toward transplantation as compared to targeting by centrality.

Rationale: Previous studies have shown that barriers to transplantation tend to be less about information but rather behaviors related to completing the transplant steps^{1,2,4,13}, thus dense social networks are likely to be more effective in changing behavior and participating in a social network than diffuse networks, which are more effective at spreading novel information³²⁻³⁴.

Patient Recruitment, Eligibility, and Retention AIM 3: One year after the initial survey, we will use a targeted network intervention to measure the spread of information, attitudes, and behaviors. We will target transplant eligible patients based on their clustering coefficient or their betweenness centrality to participate in the COACH education using data collected in AIMS 1 and 2.

Recruitment Goals: Based on previous research^{1,4}, we anticipate approximately half the patients would be eligible for a kidney transplant but not on the list. If 250 patients participate in **AIM 1 and 2**, then at least 125, or approximately 10 patients per shift will be eligible for the intervention. The intervention will target either the two most central transplant eligible patients or the two most clustered patients to participate in the COACH education. As this is a social network intervention, although we are targeting only two patients per shift, all the patients on that shift are considered exposed to the COACH education. To prevent selecting a patient that is both relatively central and clustered, the patients selected by centrality will have a centrality greater than 1 standard deviation (SD) from the mean and a clustering less than 1 SD from the mean. Conversely, the

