patient selected by clustering, will have a clustering coefficient greater than 1 SD from the mean and centrality 1 SD less than a mean. In our previous study, there was no correlation between clustering and centrality ($r=0.024$, $p=0.875$). The research and clinical staff will be blinded to whether the patient was chosen to participate in COACH because of clustering or centrality. Patients will be excluded if they are ineligible for a kidney transplant, had a previous kidney transplant, or have an active living donor.

Assignment of Intervention groups: The intervention assignment will be alternated between MWF and TTS (Table 3) to avoid patient differences between those respective days (for example patients on MWF may have been on dialysis longer while patients on TTS may be more likely to work)⁵⁵.

Retention/Attrition: **AIM3** will be carried out over the course of a year with a possible drop-out rate of 5% (Death and Transfer). If a patient transfers, the patient will be contacted via phone to do a follow-up survey.

Participant Remuneration: All patients will receive \$10 for the initial survey (Wave 1), and Wave 2 survey, \$10 for the 3 month follow-up (Wave 3), and \$10 for Wave 4. Patients will not receive remuneration for participating in the COACH education but will be able to keep the handouts and reading materials.

Data Collection (AIM 3)

Education Intervention: COACH is a behavioral communication intervention designed specifically for ESRD patients pursuing kidney transplantation. The COACH program (appendix) consists of four modules: 1) Kidney transplant options, 2) Discussing your transplant options, 3) Requesting living donation, and 4) Maintaining positive relationships. The content and teaching strategies were guided by the concepts of social cognitive theory as well as principles of adult learning and communication skill acquisition^{31,56,57}. A study coordinator will conduct the intervention in four, face to face, one hour sessions in the HD clinic. Patients will receive the a handbook and video for the COACH intervention.

Shift	Clinic 1		Clinic 2	
	MWF1	TTS1	MWF2	TTS2
1st 5am-9am	Cluster	Central	Central	Cluster
2nd 9am-1pm	Cluster	Central	Central	Cluster
3rd 1pm-5pm	Cluster	Central	Central	Cluster

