Staggered Surveys: We propose a pre-post design to assess the impact of the COACH education on patients' transplant-related knowledge and behaviors. Before administering the COACH education, we will survey targeted patients to assess changes in knowledge and behaviors towards transplant from the baseline survey. As another measure of the impact of the COACH intervention, patients not receiving the intervention will serve as controls and will be surveyed along with those receiving the intervention; we will then assess within and between group differences in transplant-related knowledge and behaviors. To assess the dissemination of information contained in the COACH intervention, all patients will be surveyed at 3-months post-intervention. The follow-up surveys will determine the sources of these changes (eg. self-reading after the survey, the COACH intervention, or discussing with other patients). Finally, during Year 4, one year post-intervention, a final survey will be administered to the all the patients in both clinics to assess retention of information and change in attitudes and behaviors of those who participated in COACH and the spread of information and behaviors to the patients who were not targeted.

Clinical Data: In addition to the survey data, we will collect patient transplant listing status, living donor evaluations from participants' respective transplant centers.

Analytic plan AIM3: To test **H3** we will assess the successful spread of the intervention by evaluating the difference in the primary outcome of completion of steps toward transplantation between patients being exposed via the most clustered (Cluster) members versus the most central (Central). We will use repeated surveys to measure our secondary outcomes include change in knowledge, attitudes, behaviors of the patients either directly exposed to the intervention or those who were exposed indirectly through the social network.

Primary Outcomes: 1) Differences in patient knowledge, 2) Differences in transplant steps completed

Secondary Outcomes: 1) Completion of transplant work-up, 2) Asking for a living donor

Independent Variables: Intervention assignment to Cluster or Central

Covariates: Age, Marital Status, insurance, transplant eligibility, HD shift, HD Clinic, network attributes

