Exposure: While only two patients per shift will receive the COACH intervention, all patients regardless of participation in the COACH education will be analyzed as exposed to the intervention via social spread. This will result in two groups for the primary analysis Cluster (MWF1 Cluster + TTS2 Cluster) and Central (MWF2 Central + TTS1 Central)

Analysis: To measure global changes, we will use a t-test to test changes in knowledge and changes in completion of steps between Cluster and Central. Individual level transfer of information will be analyzed with a

Markov chain Monte Carlo accept-reject procedure in the chain⁵⁸. We will examine the correlation in changes of a patient's(ego) knowledge with his or her first degree alter and measure the decay in correlation as the degree of the alter increases. We will also examine the ego's distance (how many links the patients are from each other) from the alter receiving the intervention. In addition, we will use Gaussian Conditional Random Fields (GCRF) methods to model a patient's stage in the transplant process by taking into account various factors such as personal demographics, social influence of alters, and global trends of HD shift and clinic⁵⁹. We will examine the characteristics of the patients disseminate and receive information. The data directly measuring the spread of information, influence, and behavior within the network from this experiment will be used to validate and strengthen the social network model developed in AIM1 and AIM2.

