Future Directions: This research will provide [name] with novel data in a critically-important and poorly-understood area of nephrology and equip him with the experience and tools to successfully compete for external funding and transition to independence as a clinician scientist. In addition to improving access to transplant, many other aspects of ESRD are behavioral, such as adherence to dialysis prescription, interdialytic weight gain, diet, medication and even choice of modality. Beyond ESRD, these methods could be used to improve kidney disease awareness, education, as well as medication adherence, especially transplant medication. The next step after this pilot study is to perform a large national study to examine the regional differences in hemodialysis clinic social networks, how these differences explain transplant disparities, and how the social networks can be engineered to improve access to transplant.

Timeline: The completion of the research is feasible in a 5 year timeline

Year	1				2				3				4				5			
Quarter	1	2	3	4	1	2	3	4	1	2	3	4	1	2	3	4	1	2	3	4
IRB review and modifications	X				X				X				X				X			
Train Research Assistant				X																
Survey by Wave 1,2,3,4					1				2	3			4							
AIM 1					X	X	X	X												
Collection of Follow-up data for AIM2					X	X	X	X	X	X	X	X								
Network Experiment AIM3									X	X	X	X	X							
Final Analysis														X	X	X	X	X		
Report to NIDDK				X				X				X				X				X

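### The Aim 3 spread analyses are not tied to the pre-COACH network, so ties formed after COACH could be counted as exposure

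*SAP*

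**What the plan says.** **Updating rule.** SAP, Approach to AIM 1, Analysis: "We will refine our network model by adding and removing links with each wave of the survey". No wave is excluded. Each survey can supply links, because the DPTQ asks patients whom they talk to in the clinic (Protocol section 4).

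**Timing.** The SAP Timeline row "Survey by Wave 1,2,3,4" puts Wave 1 in Year 2 Q1, Wave 2 in Year 3 Q1, Wave 3 in Year 3 Q2 and Wave 4 in Year 4 Q1. On COACH, the Aim 3 recruitment paragraph says "One year after the initial survey, we will use a targeted network intervention to measure the spread of information, attitudes, and behaviors", which is Year 3. Under Staggered Surveys, "all patients will be surveyed at 3-months post-intervention"; Participant Remuneration for Aim 3 labels that survey "3 month follow-up (Wave 3". Then "during Year 4, one year post-intervention, a final survey will be administered". Waves 3 and 4 therefore follow COACH, and both cover all patients.

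**Use in Aim 3.** The Aim 3 Analysis correlates an ego's knowledge change with that of first-degree alters and looks for decay at higher degrees. It adds: "We will also examine the ego's distance (how many links the patients are from each other) from the alter receiving the intervention". No wave or date is given for the network behind these measures, or for the alters in the GCRF model. The Aim 3 covariate list includes network attributes, also undated. Only the choice of whom to train is explicitly tied to Aim 1 and 2 data.

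**Purpose.** The Aim 2 Limitations paragraph concedes that Aims 1 and 2 cannot tell like-minded tie formation from spread, and gives this as the reason for Aim 3.

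**The concern.** A tie first recorded at Wave 3 or 4 may be partly a result of COACH and of the patient's own interest in transplantation. Suppose patients who became more interested, or learned more for any reason, then sought out a trained patient. In an updated network they sit close to that patient because they gained; they did not gain because they were close. A regression of gain on distance would read this as transfer. Likewise, if untrained patients with similar gains start talking to each other, ego-alter correlation will be higher at degree one than at degrees two and three, which is the decay that the Aim 3 Analysis looks for. An adjusted model using post-COACH network attributes would be conditioning on something measured after treatment.

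At stake is the purpose the SAP gives Aim 3. If exposure may include ties formed after the intervention, the ambiguity conceded for Aims 1 and 2 returns in the analyses meant to resolve it. Leaving the network undated also lets the choice be made after results are seen.

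**Working it through.** **The plan's own figures.** The SAP gives none for the distance or ego-alter analyses. Its Aim 3 sample sizes concern Cluster v Central. The stated 15 per arm does follow from the stated effect size of 1.06 (two-sample t-test, two-sided 0.05: 14.99 per arm, power 0.80), but has no bearing on this point.

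**Does the updating rule reach past COACH?** It sits under Aim 1, whose Timeline bar covers Year 2 only. Just one wave falls in Year 2, so a rule about each wave cannot sensibly stop there. Aim 2 follow-up runs to Year 3 Q4, while Aim 3 starts in Year 3 Q1. Protocol section 7.d.i gives a different schedule (three annual surveys, plus a post-intervention survey for COACH patients only), which should be reconciled with 7.d.v and the SAP. On that schedule too, at least one survey follows COACH.

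**Simulation with no spread: inputs from the documents**
- 252 expected participants over 12 shifts: 252/12 = 21 per shift.
- Two trained patients per shift (SAP; Protocol 7.d.iv says one).
- Direct COACH effect on knowledge of 1.2 SD, given to trained patients only.
- Significance level 0.05.

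**Inputs that are assumptions**
- Mean of 2.5 ties per patient; 25% or 50% of links replaced after COACH.
- Log-odds of a new tie to a trained patient rise by 0, 0.25, 0.5 or 1.0 per SD of the untrained patient's own gain. Odds ratios: exp(0.25) = 1.28, exp(0.5) = 1.65, exp(1) = 2.72.
- Homophily slope (preference for new ties between untrained patients with similar gains) of 0, 0.5 or 1.

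**Test.** Untrained patients' gain is regressed on distance to the nearest trained patient (capped at 4), with shift fixed effects and 600 runs per setting. Simulation error at 5%: 1.96 × √(0.05 × 0.95/600) = 1.7 points.

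Percentage of no-spread runs in which the test rejects:

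| Odds ratio per SD of own gain | Homophily slope | Updated links, 25% / 50% replaced | Pre-COACH links, same runs |
|---|---|---|---|
| 1.00 | 0 | 4.5 / 5.5 | 5.5 / 4.7 |
| 1.28 | 0 | 6.5 / 7.2 | 5.0 / 4.2 |
| 1.65 | 0 | 7.0 / 19.5 | 4.5 / 4.7 |
| 2.72 | 0 | 27.2 / 66.8 | 3.7 / 5.8 |
| 1.00 | 0.5 | 6.8 / 8.2 | 6.5 / 4.0 |
| 1.65 | 0.5 | 9.0 / 26.3 | 4.3 / 4.3 |
| 2.72 | 1 | 25.5 / 80.0 | 3.7 / 5.3 |

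Random link changes give no bias. At odds ratios of 1.65 and above, nearly all rejections point to closer meaning more gain.

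**Decay by degree.** Centring on 21 − 2 = 19 untrained patients per shift gives an expected correlation of −1/18 = −0.056 under no association. Pre-COACH links stay near this at degrees 1, 2 and 3. Updated links with 50% replaced and homophily slope 0.5 (odds ratio 1.00) give +0.07, −0.06 and −0.07. With slope 1 and odds ratio 2.72 they give +0.14, −0.04 and −0.11. This is decay without spread.

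**Sensitivity to design.** A cruder t-test (direct tie to a trained patient v none) with 25 per shift and a 10% base chance of a new tie rejects in 9%, 24% and 80% of runs at log-odds 0.25, 0.5 and 1.0. With 21 per shift the middle figure falls to about 16%.

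**What fixing the network does not do.** In a further no-spread simulation at 21 per shift, an interest trait raises both baseline ties to trained patients (log-odds 0.5 to 1.0 per SD) and knowledge gain (correlation 0.3 to 0.5), all assumed. The pre-COACH network then rejects falsely in 16% to 89% of runs (about 18% to 92% in a repeat). The updated network, with random link change after COACH, rejects in 10% to 59%.

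**The case against.** The strongest reply is that the updating sentence belongs to Aim 1 and nothing says Aim 3 distance uses Wave 3 or 4 links. The text may even lean the other way: trained patients are chosen from Aim 1 and 2 data, and the Aim 3 Analysis treats the Aim 1 and 2 model as something already built, to be validated. This stands as far as it goes. A reader might infer that the plan prescribes a post-treatment exposure, and it does not; it leaves the network open. But the reference to the earlier model is not a rule for measuring distance, and an open choice needs closing.

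The second reply is that H3 is tested by Cluster v Central, grouped by assigned shift, with everyone on the shift counted as exposed. That is right. A reader might infer that the main comparison is biased, but no network wave enters that t-test and it has no covariates.

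The third is that the mechanism is partly conjecture. No passage says COACH creates ties with fellow dialysis patients, or does so selectively with those who gain most. COACH is a communication intervention with a module on discussing transplant options, so the mechanism is plausible, not shown. It is also tempting to argue that the source-of-knowledge item ("The follow-up surveys will determine the sources of these changes (eg. self-reading after the survey, the COACH intervention, or discussing with other patients") prompts patients to name such ties. The documents do not show that it asks for names, and the SAP presents it as a safeguard. The observed-interaction log verifies and weights survey links, but would not exclude real ties formed after COACH.

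Updating links is also legitimate in a model of tie change. The temporal ERGM is such a tool, but it is specified for Aim 2; nothing comparable is specified for Aim 3 distance or decay.

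**Conclusion.** The concern holds for the individual-level spread analyses only: ego-alter correlation, its decay, distance to the trained patient, and any Aim 3 model using undated alters or network attributes. As written, the plan allows ties formed after COACH to define exposure. A false signal can then appear; the documents do not show that it will. It requires link changes related to a patient's own interest or gain, and random change produces none.

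The rejection rates rest on assumed tie formation, for which the documents give no value. They show direction and a possible range, and are not error rates to expect in this trial. Nor does it follow that a fixed network makes the spread analyses free of confounding: the nominal error in the table depends on gain being unrelated to baseline ties. Fixing the network removes selection that arises after COACH and leaves like-mindedness already in the baseline ties. The change is worth making because it is cheap and bears on the reason the SAP gives for Aim 3.

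**What to change.** Add to the Aim 3 Analysis that alter degree, distance to trained patients and all network covariates (including clustering and centrality) are computed once per shift from links recorded before the first COACH session on that shift: survey links through Wave 2, and interaction logs up to that date. The session date should be the cut-off because Wave 2 and the start of Aim 3 share a quarter in the Timeline. Apply the same network to the GCRF model. Analyse links first recorded afterwards separately, as an outcome (new ties after COACH).

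State as a limitation that this removes only post-COACH tie selection and does not separate spread from like-mindedness already present in baseline ties.

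The cost is SAP wording and dated link records; no new data are needed. The downside is that patients tied to a trained patient only after COACH are classed as distant, which may slightly understate true transfer.

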Survey Instrument: The *Dialysis Patient Transplant Questionnaire* (DPTQ) includes a mix of 49 questions, single measures, and scales previously validated in HD and transplant populations and items developed to address the co-investigators' specific research interests (see appendix). The DPTQ has demonstrated construct validity in previous studies^{1,4,11,12}. It includes 17 items on communication confidence developed specifically to evaluate the COACH program and rated along a scale from 0 to 100 (Cronbach's alpha = .90); summed to create a composite confidence score. In addition, there are 12 true/false items on transplant knowledge items; correctly answered items are summed to create a composite knowledge score. The questionnaire will also include questions regarding medical conditions which may preclude the patient from transplantation. Clinic staff will also participate in a modified version of the survey to assess their attitudes towards HD^{48,49} and kidney transplantation, during Year 2.

Participant HD Seating and Observed Interaction Log: Patient seating assignments will be recorded, as well as, the staff observed social interaction log, which documents the frequency, duration, and nature of observed patient-patient interactions (appendix).

Clinical Data: Upon consent, routine HD laboratory and clinical data (including co-morbid conditions, e.g. diabetes, congestive heart failure, cardiovascular disease, chronic obstructive pulmonary disease, and malignancy, which will be reconciled with survey data) will be extracted from the DARWIN database by the DCI Information Technology Department. Data will be downloaded, cleaned, merged, and submitted for preliminary analysis. Patient's steps to transplantation (Table 2)^{1,2} will be recorded and listing status will be verified with the patient transplant center or centers (**AIM 2**).

Analytic Plan AIM1: To test **H1**, we will create nodal network graphs (Figure 1, for example) using data collected from the patient and staff surveys, and clinical observations. We will characterize and compare the structure of the patient HD clinic networks by gender and race. We will assign demographic, survey, and clinical data abstracted from the EMR to each node in the network.

Primary outcome: Differences in clustering and centrality by gender and race (**H1**)

Independent Variables: Sex and Race

Covariates: Age, Marital Status, HD vintage, insurance, HD Clinic, and HD shift

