Analytic Plan AIM 2: To test **H2**, we will use the network information from Aim 1 to analyze correlation of knowledge, attitudes, and behaviors between members of the network (transplant discussions, living donor recruitment, and step in kidney transplant process) from the surveys and the EMR.

Primary Outcome: Correlation of 1) attitudes about transplantation and 2) step in transplant process

Independent Variables: Clustering coefficient and attributes of alters

Covariates: Age, Marital Status, HD vintage, insurance, transplant eligibility, HD clinic, network attributes

Analysis: We will examine how knowledge, attitudes, and completion of steps differ by network attributes. These differences will then be validated by using logistic regression modeling to predict patient's attitudes towards transplantation and step in the transplant work-up using demographic and survey variables. We will then add network attributes and quantify the improvement in the prediction model using tests for goodness of fit. To further validate the model we will perform an Exponential Random Graph Model (ERGM) with temporal attributes⁵³ in which the patients current transplant step is a function of patients baseline data and network attribute as well as their alters' baseline step, current step, and network attributes.

Limitations: We have previously found that patients are often incorrect about their listing status⁴, thus we will confirm the transplant status by contacting the listing institution. Using the steps completed will allow for the analysis of patients that are highly motivated who complete all their work-up but are discovered to have an absolute contraindication to transplantation. Since AIM 1 and 2 are observational, we will be unable to determine whether patients form small networks with like-minded individuals or whether over time everyone in a small network will reach a common belief through spread of information and behaviors⁵⁴. To test the spread of information and behaviors, in **AIM 3**, we will use a network targeted intervention.

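### Aim 2 measures similarity between network members but omits HD shift and has no same-shift reference, so residual shift-level similarity cannot be separated from network similarity

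*SAP*

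**What the plan says.** SAP section 3.C, Analytic Plan AIM 2, gives the primary outcome as "Correlation of 1) attitudes about transplantation and 2) step in transplant process", taken between members of the network. The predictors are given as "Independent Variables: Clustering coefficient and attributes of alters".

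The three covariate lists differ on shift:

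- Aim 1: "Covariates: Age, Marital Status, HD vintage, insurance, HD Clinic, and HD shift"
- Aim 2: "Covariates: Age, Marital Status, HD vintage, insurance, transplant eligibility, HD clinic, network attributes"
- Aim 3: "Covariates: Age, Marital Status, insurance, transplant eligibility, HD shift, HD Clinic, network attributes"

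The Aim 3 list names shift and network attributes separately, so the network-attributes entry in Aim 2 cannot be read as covering shift.

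The Aim 2 analysis starts with regression on demographic and survey variables, then adds network attributes, then fits a temporal exponential random graph model (ERGM). It specifies no shift effect, no untied same-shift pairs and no within-shift reference distribution. The comparator it does have is in H2, which sets dense networks against diffuse ones ("completion of steps to kidney transplant as compared to patients diffuse networks"). The Aim 2 limitations distinguish like-minded patients grouping together from beliefs spreading through a group. They do not mention a shared shift environment.

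Under AIM 3, Assignment of Intervention groups, the SAP gives an example of how the two weekly schedules may differ: "patients on MWF may have been on dialysis longer while patients on TTS may be more likely to work".

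**The concern.** Two patients on the same shift can resemble each other for three reasons: they chose each other, one influenced the other, or both are exposed to the same shift conditions. Aim 2 acknowledges the first two only. The SAP's Significance section describes contact as arising from long sessions in assigned neighbouring seats, so most ties are probably between patients on the same shift. Tied pairs then carry whatever shift-level similarity the covariates leave behind, and the plan offers nothing to subtract it from.

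Of the two schedule differences the SAP names, dialysis vintage is an Aim 2 covariate but work status is not. Aim 2 is the aim that correlates patients with one another, and it is the only one of the three without shift. At stake is whether a positive ego-alter correlation, or a positive coefficient on alters' attributes, can be read as evidence about ties at all.

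**Working it through.** **1. Inputs and the plan's own figure.** Census 280 (Setting) and a response rate of 90% (Recruitment Goals) give 280 × 0.90 = 252, the SAP's expected sample. Two clinics with six shifts each make 12 shifts, and 252 / 12 = 21 patients per shift. The significance level is 0.05 (Protocol 7.d.vi). Aim 2 states no power, effect size or target correlation, so there is nothing further to reproduce.

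**2. Expected correlation with no network effect.** Let ρ be the share of outcome variance due to shift after the other covariates. Centre on the clinic mean (6 shifts, 126 patients). For any two patients on the same shift, tied or not:

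- covariance = ρ × 5/6 − (1 − ρ)/126
- variance = ρ × 5/6 + (1 − ρ) × 125/126

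At ρ = 0.05 the ratio is 0.0341 / 0.9841 = 0.035. At ρ = 0.10 it is 0.0762 / 0.9762 = 0.078. Ties play no part in the formula.

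**3. False-positive rate.** Simulation of 12 shifts of 21, with a clinic difference, a shift effect, no influence along ties, and all ties within shift. The network has five sub-networks of four per shift, three fully connected and two star-shaped (24 ties per shift). There were 400 runs with 199 permutations each, permuting either within clinic (the clinic adjustment in the Aim 2 list) or within shift.

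| Shift ICC (assumed) | Mean r, tied pairs | Mean r, untied same-shift pairs | Rejects, within clinic | Rejects, within shift |
|---|---|---|---|---|
| 0 | −0.01 | −0.01 | 6.8% | 5.8% |
| 0.02 | 0.01 | 0.01 | 8.5% | 4.0% |
| 0.05 | 0.03 | 0.04 | 12.2% | 3.7% |
| 0.10 | 0.07 | 0.07 | 26.3% | 4.5% |
| 0.20 | 0.16 | 0.16 | 65.7% | 4.5% |

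The Monte Carlo standard error at 5% is √(0.05 × 0.95 / 400) = 1.1 points. Tied and untied same-shift pairs are equally correlated, so the apparent similarity is all shift.

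A check with ties placed at random within shift, four per patient (21 × 4 / 2 = 42 ties per shift, 1,000 runs), gave 5.4%, 6.7%, 16.5%, 40.2% and 81.0% with clinic adjustment and 4.1-5.8% within shift. Taken with other random layouts, the rates are about 6-9%, 12-18%, 26-40% and 66-83% at ICC 0.02, 0.05, 0.10 and 0.20. These are not ceilings: five ties per patient gave 47.5% at 0.10.

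**4. The H2 contrast.** In the network of the table, the dense-minus-diffuse difference in correlation was −0.003 to 0.018 when both kinds of tie lay within shift, which is essentially no bias. When half the diffuse ties crossed shifts within a clinic, it was 0.05, 0.06 and 0.11 at ICC 0.05, 0.10 and 0.20.

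**5. Where the shift-adjusted correlation centres.** Residuals centred on a shift of 21 have expected pair correlation −1/(21 − 1) = −0.05. The simulated means were −0.048 to −0.053. Zero is therefore the wrong null value after shift adjustment.

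**6. How large the ICC might be.** The documents give no value. One partial anchor applies to Year 3. The Timeline has Aim 2 follow-up overlapping the Aim 3 experiment, whose arms are assigned by schedule within clinic (Table 3), so clinic cannot absorb arm. The Aim 3 sample-size section expects a 2-step arm difference (SD 1.5 and 1.7) and claims power for 1 step. The pooled variance is (1.5² + 1.7²)/2 = 2.57. The variance share of arm would be 1² / (1² + 2.57) = 0.28 for 2 steps and 0.5² / (0.5² + 2.57) = 0.09 for 1 step. This holds only among eligible patients and only if H3 is true. It says nothing about baseline.

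**The case against.** The case against has five parts.

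- **Most obvious shift differences are already adjusted for.** Age, marital status, vintage, insurance, eligibility and clinic are covariates. The SAP's remark on patient mix concerns the two weekly schedules, not 12 shifts, and is worded as a possibility. This stands: only the residual can leak, and its size is unknown.
- **H2 is a contrast, not a single correlation.** If both kinds of tie lie within shift, the shift component largely cancels (step 4). This also stands. It does not protect the raw member correlation, which is the named primary outcome, or the alter-attribute terms.
- **The ERGM conditions on baseline.** It uses the patient's baseline data and alters' baseline step, which should absorb part of a stable shift difference. This is partial cover for one model.
- **Moran statistics and permutation schemes are not Aim 2 methods.** The sentence "For continuous variables, testing distances and similarities, Moran statistics will be calculated" belongs to Aim 1, where shift is a covariate, and the SAP nowhere proposes free reshuffling of all patients. This is correct. The gap in Aim 2 is that no reference is specified. The Aim 1 bootstrap addresses the variability of estimates and would not remove a common shift mean.
- **The remedy may hide real effects.** Aim 3 treats everyone on a shift as exposed through the network, so within-shift comparison discards influence that reaches the whole shift evenly. This is a real cost. Similarity specific to ties remains detectable.

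**Conclusion.** The point holds in a limited form. Aim 2 omits HD shift, although Aims 1 and 3 include it, and names no untied same-shift reference. Residual shift-level similarity is therefore confounded with network similarity in the ego-alter correlations and alter-attribute terms. The inflation is slight at a shift ICC of 0.02, two to four times nominal at 0.05, and large from 0.10 upward. H2's contrast is at risk mainly if density is linked to shift or diffuse ties cross shifts.

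These sizes rest on assumptions that are not in the documents: the ICC (0 to 0.20), ties mostly within shift, equal enrolment of 21 per shift, and the simulated network layouts.

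A reader might go further in two ways, and the documents support neither. One is that anything patients on a shift share will be reported as network similarity. The listed covariates remove part of it, including vintage. The other is that the error passes into the Aim 3 model. Aim 3 lists shift as a covariate, and its Gaussian conditional random field model includes shift and clinic trends. What it takes forward for targeting is clustering and centrality, not Aim 2 correlations. The stated plan is for Aim 3 data to validate the earlier model, not the reverse.

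**What to change.** Three changes to Analytic Plan AIM 2:

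1. Replace HD clinic in the covariate list by HD shift, defined as clinic by day schedule by time of day (12 levels). Clinic is fully determined by this factor, so the two cannot both be fitted as fixed effects.
2. State that tied-pair correlations of attitude and step are judged against permutation of patient values within shift, or against untied pairs on the same shift. This is meant for the tied-pair correlations, not for every p-value and interval in Aim 2.
3. State that shift-adjusted residual correlations are not tested against zero, because with 21 patients per shift they centre near −0.05.

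Report the unadjusted correlation beside the within-shift result, so that influence spread evenly over a whole shift stays visible even though it is no longer credited to ties. Add shared shift environment to the Aim 2 limitations as a third explanation.

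The cost is a few lines of SAP text and code, and 10 more model parameters (11 for shift in place of 1 for clinic). No new data are needed: shift is already an Aim 1 and Aim 3 covariate, and seating is recorded.
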